3 METHODOLOGY

3.1 Summary of Study Design

This is a multicenter non-interventional cross-sectional study in stage IV NSCLC patients on first-line systemic treatment coming to the consultation.

Consecutive patients with metastatic stage IV NSCLC selected for systemic treatment or best supportive care will be included in the trial at the time the patient signed the informed consent form (ICF). Patients that were selected for systemic treatment, should have received at least their first dose and a maximum of one cycle of the same treatment.

The pneumo-oncologist that treats the patient will fill in the CRF, indicating the systemic treatment option and the link with the variable categories that impacted positively or negatively the systemic treatment option. The actual value of variables linked to a variable category will also be recorded in the CRF.

A questionnaire has to be filled in characterizing the site and allowing the site to be assigned to a group based on the number of newly diagnosed patients per year with lung cancer and whether the site participates in interventional clinical trials. All sites will be retrospectively divided in four groups; high number of patients per year (more than median NSCLC patients per year) and participating in interventional clinical trials, high number of patients but not participating in interventional clinical trials, low number of patients (less than median NSCLC patients per year) and participating in interventional clinical trials or low number of patients and not participating in interventional clinical trials.

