4.2 Covariates

The actual values of the following covariates will be recorded within the eCRF, which can be discrete or continuous in nature. In addition to the actual values, the investigator will also have to indicate whether the covariates had an impact on the treatment choice in a binary fashion.

✓ Patient demography characteristics at study entry:

- Age
- Gender:
 - F
 - M
- Weight loss
 - (%)
- Smoking status:
 - Current
 - Former (≥ 1 year)
 - Never
 - Not known
- ECOG status:
 - 0
 - 1
 - 2
 - 3-4
- Patient's preference
 - Yes
 - No

✓ Medical history:

- Metastatic disease stage:
 - M1a
 - M1b

- M1c
- Tumor Burden:
 - Tumor size
 - Number of metastatic sites
- Brainmets:
 - No
 - Symptomatic
 - Asymptomatic
 - Treated with SRT
 - Treated with WBRT
- Livermets
 - Present
 - Not present
- Concomitant malignancies
 - Present
- Histology:
 - Squamous
 - Nonsquamous
 - NOS
- IHC PD-L1:
 - PD-L1 TPS <1%,
 - PD-L1 TPS 1 - 49%
 - PD-L1 TPS ≥50%
- High TMB (≥ 10 mutations/Mb (Cfr. CHECKMATE-227))
 - Present
 - Not present
- Testing
 - Turn-around-time
 - Not tested
 - Biopsy availability
 - Type of NGS testing (e.g. whole exome, gene panel, platform, ...)

- ✓ Comorbidities
 - Myocardial infarction in the last year
 - Congestive heart failure
 - Peripheral vascular disease
 - Hypertension
 - Cerebrovascular event in the last year
 - Transient ischemic attack in the last year
 - Diabetes without complications
 - Renal disease
 - Liver disease
 - Hematological disease
 - Chronic obstructive pulmonary disease
 - Chronic infections
 - Mental disorders

- ✓ Autoimmune disease
 - Active inflammatory interstitial lung disease
 - Non-active inflammatory interstitial lung disease
 - Active inflammatory bowel disease (IBD)
 - Non-active IBD
 - Active inflammatory joint disease
 - Non-active inflammatory joint disease
 - Active psoriasis
 - Non-active psoriasis
 - Active connective tissue disease
 - Non-active connective tissue disease

- ✓ Current/recent medication
 - Low dose corticosteroids
 - High dose (≥ 10 mg/day Prednisolone or eq) corticosteroids
 - Other immunosuppressants (i.e. Anti-TNF- α , MMF, ...)
 - Antibiotics

- ✓ Prior cancer treatment in earlier stage NSCLC
 - Single Modality treatment
 - Multi-Modality treatment
 - Surgery / radiotherapy
 - Previous IO treatment
 - Year of treatment

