For each variable category, the physician has to determine whether it had an impact on his/her treatment decision, yes or no. For all variable categories, for whom the answer was yes, the physician has to select the three most important variable categories that impacted his treatment decision.

5 Study Flow Chart

	V1	V2*
Informed consent	X	
Inclusion	X	
Exclusion	X	
Systemic treatment option		X
Variable categories impacting treatment choice		X
Patient demography characteristics		X
Medical history		X
Co-morbidities		X
Autoimmune disease		X
Baseline medications		X
Prior cancer treatment in earlier stage		X
Site characteristics		X

*time of V2 and V1 can coincide. V2 will only be created if V1 is successfully passed.

It is allowed that information is collected retrospectively.

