9.1 Statistical Methods

The statistical analysis will be performed using SAS software 9.2.

9.1.1 Primary Objective(s): Calculation of Epidemiological Measure(s) of Interest (e.g. descriptive statistics, hazard ratios, incidence rates, test/retest reliability)

Systemic treatment choices and best supportive care are defined as :

- 1) Chemotherapy (chemo)
- 2) Immunotherapy (IO)
- 3) immuno combined therapies (IO+IO)
- 4) IO+chemo
- 5) IO+bevacizumab+chemo (IO+bev+chemo)
- 6) best supportive care (BSC).

Descriptive statistics of the relation between variable category and systemic treatment choice will be provided. The descriptive statistics will involve the number of times (frequency) a variable category is indicated as being linked to a systemic treatment option.

For each of the variable categories that are linked to a systemic treatment choice, descriptive statistics of the underlying variables will be provided. These descriptive statistics will consist of:

- For the quantitative variables, summary statistics including mean, standard deviation, 95% confidence interval on the mean, minimum, first quartile, median, third quartile, maximum, and number of available and number of missing observations.
- For the categorical variables, frequencies and percentages.

In an exploratory analysis, a penalized hierarchical logistic regression model for discrete choices will be used to evaluate the effect of the potential explanatory variables on the 1st line systemic treatment.

9.1.2 Secondary Objective(s): Calculation of Epidemiological Measure(s) of Interest (e.g. hazard ratios, incidence rates, test/retest reliability)

No secondary objectives.

9.1.3 Exploratory Objective(s): Calculation of Epidemiological Measure(s) of Interest (e.g. hazard ratios, incidence rates, test/retest reliability)

Investigate if there are differences in the link between variable categories and systemic treatment choices for the 4 types of sites that are defined.

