1.5.2 Patient Characteristics

After making the treatment choice, the investigator records the following variables and indicates whether the characteristic impacted the treatment choice (yes/no). Of the variables indicated as having an impact, the investigator chooses at least one and a maximum of three most important characteristics.

Demographic data

- Age (years)
- Gender (male/female)
- Weight loss (%)
- Smoking status (current/former (≥ 1 year)/never/unknown¹)
- ECOG status (0/1/2/3-4/unknown¹)
- Patients' preference for treatment choice (yes/no/unknown¹)

Medical history

- Metastatic disease status (M1a/M1b/M1c/unknown¹)
- Tumor burden:
 - Tumor size diameter (mm)
 - Number of metastatic sites
- Brainmets (yes/no), if yes:
 - Symptomatic/asymptomatic
 - Treated with SRT/treated with WBRT/not treated
- Livermets (present/not present/unknown¹)
- Concomitant malignancies (present/not present/unknown¹)
- Histology (squamous/non-squamous/not otherwise specified¹)
- IHC PD-L1 (PD-L1 TPS $< 1\%$ / $1-49\%$ / $\geq 50\%$ / unknown¹)
- High TMB (≥ 10 mutations/Mb) (present/not present/unknown¹)
- Genetic testing complications (turnaround time/biopsy availability/not tested¹/not applicable¹)

Co-morbidities

Presence (yes/no) of the following diseases:

- Myocardial infarction in the last year
- Congestive heart failure
- Peripheral vascular disease
- Hypertension
- Cerebrovascular event in the last year
- Transient ischemic attack in the last year
- Diabetes with complications
- Renal disease
- Liver disease
- Hematological disease
- Chronic obstructive pulmonary disease
- Chronic infections
- Mental disorders

¹ Considered missing in the analysis

Autoimmune disease

Presence, and in case present, active (yes/no), of the following diseases:

- Inflammatory interstitial lung disease
- Inflammatory bowel disease (IBD)
- Inflammatory joint disease
- Psoriasis
- Connective tissue disease

Current/recent medication

- Corticosteroids (yes/no), and if yes, low dose/high dose (≥ 10 mg/day Prednisolone or equivalent)
- Other immunosuppressants
- Antibiotics

Prior cancer treatment in earlier stage NSCLC

Did the patient undergo the following treatment (yes/no) and if yes, the year of the treatment:

- Single-modality treatment
- Multi-modality treatment
- Surgery/radiotherapy
- Previous IO treatment

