2.4 Impact of Covariates on the Outcome Variable

For each variable for which the impact has been evaluated, frequency distributions will be given of the impact, for all patients and per level of the outcome variable (treatment choice).

Demographic data

- Age and Weight loss
- Gender, Smoking status, and ECOG
- Patients' preference for treatment choice

Medical history

- Metastatic disease status
- Tumor size diameter and Number of metastatic sites
- Brainmets, Symptomatic/asymptomatic, and Treatment
- Livermets, Concomitant malignancies, Histology, IHC PD-L1, High TMB, and Genetic testing complications

Co-morbidities

- Each Co-morbidity

Auto-immune disease

- Presence and activity of each Auto-immune disease

Current/recent medication

- Use of Corticosteroids and Dose
- Use of Other immunosuppressants and Antibiotics

Prior cancer treatment in earlier stage NSCLC

- Each Prior cancer treatment in earlier stage NSCLC

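### No planned SAP table crosses a variable's value with its impact flag, so the impact tables cannot show at which values physicians considered a characteristic to matter

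*Protocol*

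**What the plan says.** Protocol 3.1 says the treating physician records the treatment option and its link with the categories that "impacted positively or negatively the systemic treatment option", together with the actual values of the variables. The matching sentence in the protocol summary mentions no sign.

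The recorded item is unsigned throughout. Protocol 4.2 has the investigator "indicate whether the covariates had an impact on the treatment choice in a binary fashion", and then, at category level: "For each variable category, the physician has to determine whether it had an impact on his/her treatment decision, yes or no". In SAP 1.5.2 the investigator "indicates whether the characteristic impacted the treatment choice (yes/no" and picks up to three most important characteristics.

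For the primary objective, Protocol 9.1.1 plans two descriptive steps. The first is "the number of times (frequency) a variable category is indicated as being linked to a systemic treatment option". The second is: "For each of the variable categories that are linked to a systemic treatment choice, descriptive statistics of the underlying variables will be provided".

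The SAP plans two families of tables. Sections 1.8.1 (item 2) and 2.3 describe each patient characteristic in all eligible patients, by treatment and by site type. Sections 1.8.1 (item 3) and 2.4 classify impact as important, present or absent, and there "frequency distributions will be given of the impact, for all patients and per level of the outcome variable (treatment choice"). SAP 1.9 lists one departure from the protocol, the change of regression model.

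**The concern.** The impact flag is what distinguishes this study from an ordinary cross-tabulation of characteristics by treatment. To interpret it, a reader needs to know the variable's value when the physician said it mattered. A statement that age or ECOG status had an impact in some share of chemotherapy patients says little until one knows whether those patients were old or young, fit or unfit.

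The second step of Protocol 9.1.1 appears to supply this, and the SAP contains no table that does. If it was left out by oversight, one of the two descriptive steps under the primary objective has gone missing without being declared. The gap matters most for characteristics on which every patient has a value, such as age, ECOG status, PD-L1 category or tumour size. For rare present/absent conditions, a flag presumably goes with presence in most cases.

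**Working it through.** The documents state no figure on this point, so there is none to reproduce. The check compares the planned tables and then asks whether the two existing sets determine the missing one.

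**1. Planned tables side by side**

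| Analysis | Value shown | Impact shown | Split by treatment |
|---|---|---|---|
| Protocol 9.1.1, first step | no | yes | yes |
| Protocol 9.1.1, second step (patient-level reading) | yes | restricted to linked | yes |
| SAP 2.3 | yes | no | yes |
| SAP 2.4 | no | yes | yes |
| SAP 2.5 (exploratory model) | yes, as predictor | no | yes, as outcome |

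No SAP row has both value and impact.

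**2. Do SAP 2.3 and 2.4 together fix the joint distribution?** For one treatment, let n be the number of patients, a the number flagged for a variable (from 2.4) and b the number with a high value of it (from 2.3). The number x who are both flagged and high satisfies

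max(0, a + b − n) ≤ x ≤ min(a, b).

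The documents give no values for n, a or b, so these are assumed:

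| n | a | b | Range of x | Share high among flagged |
|---|---|---|---|---|
| 30 | 15 | 15 | 0 to 15 | 0% to 100% |
| 60 | 30 | 30 | 0 to 30 | 0% to 100% |
| 60 | 20 | 24 | 0 to 20 | 0% to 100% |
| 100 | 40 | 50 | 0 to 40 | 0% to 100% |

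The bounds tighten only when a + b exceeds n (lower bound above zero) or b is smaller than a (upper bound below 100%). If nearly everyone is flagged, or nearly everyone has the same value, the existing tables say more. Between those extremes they can say nothing about the flagged patients.

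**3. Two opposite situations with identical SAP tables** (n = 60, a = 30, b = 30)

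| | Flagged, high | Flagged, low | Not flagged, high | Not flagged, low | Share high among flagged |
|---|---|---|---|---|---|
| A | 27 | 3 | 3 | 27 | 27/30 = 90% |
| B | 3 | 27 | 27 | 3 | 3/30 = 10% |

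In both, SAP 2.3 prints 30 of 60 high and SAP 2.4 prints 30 of 60 flagged. In A the variable mattered mostly at high values, in B mostly at low ones. A value-by-impact table separates them.

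**4. Cell sizes for the added table.** Protocol 9.3 asks for at least 30 patients in a subgroup that is analysed. At the target of 210 patients and the four treatments observed (SAP 1.2.2):

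- three impact levels: 210 / (4 × 3) = 17.5 per cell on average;
- any impact versus none: 210 / (4 × 2) = 26.25 per cell on average;
- any impact versus none, treatments pooled: 210 / 2 = 105 per cell on average.

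A full three-level split within treatment would therefore mostly breach the rule. The two-level split will meet it in some cells and not in others.

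**The case against.** The strongest reply is textual. In the second step of Protocol 9.1.1 the selector is the category, not the patient. If a category counts as linked once any physician has flagged it, and its variables are then described in everyone, SAP 2.3 already does this and nothing has been dropped. That reading is possible, so the omission is probable rather than proven. It is the less natural reading, because the preceding sentence counts individual reported links, and because nearly every category would probably be linked at least once, leaving the restriction with almost nothing to do.

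A second reply is that SAP 2.3 and the model in 2.5 already address the primary objective. This stands in part: they show how values relate to the treatment given. They do not use the flag, so they do not show at which values physicians regarded a variable as relevant. SAP 1.8 also plans individual listings of patient characteristics, but a listing is not a summary.

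Two stronger readings are tempting. A reader might infer that the SAP is what loses the direction of impact. The documents do not support this: Protocol 4.2 and SAP 1.5.2 both record a bare yes/no, so the sign is lost at data collection. A reader might also infer that crossing value with impact would restore the direction. It would not. A flagged high age in a chemotherapy patient could have favoured chemotherapy, argued against another option, or counted against chemotherapy and been outweighed. Only a signed item could tell these apart.

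**Conclusion.** On the patient-level reading of Protocol 9.1.1, the SAP lacks the second primary descriptive step and does not declare its absence. Under either reading, no planned table shows the values among flagged patients, and the planned margins do not determine them: in the assumed cases the share with a high value runs from 0% to 100%. How much information is lost in this study cannot be quantified, since the documents do not give the share of patients flagged for any variable. The mismatch between Protocol 3.1 and the yes/no item is separate and does not depend on how 9.1.1 is read.

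This is a modest, inexpensive improvement to the primary descriptive analysis. It does not put the existing tables or the exploratory model in doubt.

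**What to change.** 1. Add to SAP 2.4, within each treatment, the descriptive statistics or frequencies of each variable's value by any impact versus no impact. Show the three impact levels only where the 30-patient rule of Protocol 9.3 is met. Where a split falls short, pool across treatments or give a listing that carries both the value and the flag. Pooling loses the link with the treatment and should be labelled accordingly. The SAP should also repeat the 30-patient rule, which it does not mention at present.
2. If the sponsor does not want this table, record the omission in SAP 1.9, or state there that 9.1.1 is read at category level and is met by SAP 2.3.
3. Reconcile the wording of Protocol 3.1 with the yes/no item. State in the SAP and the report that the direction of impact was not collected and that the added table shows at which values a variable was reported to matter, not whether it argued for or against the treatment.

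The cost is extra tables, some of them sparse, from values and flags that SAP 1.5.2 already records for each characteristic, plus a few sentences of text. Obtaining direction itself would need a signed CRF item, which is outside this fix.

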3.2 Study Population

210 eligible stage IV NSCLC subjects treated in approximately 21 Belgian hospitals starting first-line treatment or best supportive care will be enrolled in line with inclusion and exclusion criteria. The estimated recruitment period to reach the target of 210 eligible patients is 5 months. Upon inclusion of 210 eligible patients the recruitment will be closed. Only a maximum of 10% of subjects can be enrolled by one site.

3.3 Inclusion Criteria

All inclusion and exclusion criteria will be reviewed by the investigator or qualified designee to ensure that the subject qualifies for the study.

In order to be eligible for participation in this trial, the subject must:

- Have voluntarily agreed to participate by giving written informed consent/assent for the trial.

- Have a histologically or cytologically confirmed diagnosis of stage IV NSCLC on first-line (1L) systemic treatment.
- Have received at least their first dose of the selected systemic treatment and a maximum of 1 cycle of the same treatment. Patients that were selected to receive best supportive care will not have to comply to this inclusion criterion.
- Be ≥ 18 years of age on day of signing informed consent.

3.4 Exclusion Criteria

The subject must be excluded from participating in the trial if the subject:

- Has received prior systemic treatment for their metastatic NSCLC before the first dose of trial treatment. However, subjects who received adjuvant or neoadjuvant therapy during an earlier stage of their disease, but evolved to stage IV, are eligible.
- TKI selected as first-line systemic treatment.
- Is participating in an interventional trial or medical need program.

4 Variables and Epidemiological Measurements

4.1 Outcomes

Systemic treatment choices and best supportive care are defined as :

- 1) Chemotherapy (chemo)
- 2) Immunotherapy (IO)
- 3) immuno combined therapies (IO+IO)
- 4) IO+chemo
- 5) IO+bevacizumab+chemo (IO+bev+chemo)
- 6) best supportive care (BSC).

4.2 Covariates

The actual values of the following covariates will be recorded within the eCRF, which can be discrete or continuous in nature. In addition to the actual values, the investigator will also have to indicate whether the covariates had an impact on the treatment choice in a binary fashion.

✓ Patient demography characteristics at study entry:

- Age
- Gender:
 - F
 - M
- Weight loss
 - (%)
- Smoking status:
 - Current
 - Former (≥ 1 year)
 - Never
 - Not known
- ECOG status:
 - 0
 - 1
 - 2
 - 3-4
- Patient's preference
 - Yes
 - No

✓ Medical history:

- Metastatic disease stage:
 - M1a
 - M1b

- M1c
- Tumor Burden:
 - Tumor size
 - Number of metastatic sites
- Brainmets:
 - No
 - Symptomatic
 - Asymptomatic
 - Treated with SRT
 - Treated with WBRT
- Livermets
 - Present
 - Not present
- Concomitant malignancies
 - Present
- Histology:
 - Squamous
 - Nonsquamous
 - NOS
- IHC PD-L1:
 - PD-L1 TPS <1%,
 - PD-L1 TPS 1 - 49%
 - PD-L1 TPS ≥50%
- High TMB (≥ 10 mutations/Mb (Cfr. CHECKMATE-227))
 - Present
 - Not present
- Testing
 - Turn-around-time
 - Not tested
 - Biopsy availability
 - Type of NGS testing (e.g. whole exome, gene panel, platform, ...)

- ✓ Comorbidities
 - Myocardial infarction in the last year
 - Congestive heart failure
 - Peripheral vascular disease
 - Hypertension
 - Cerebrovascular event in the last year
 - Transient ischemic attack in the last year
 - Diabetes without complications
 - Renal disease
 - Liver disease
 - Hematological disease
 - Chronic obstructive pulmonary disease
 - Chronic infections
 - Mental disorders

- ✓ Autoimmune disease
 - Active inflammatory interstitial lung disease
 - Non-active inflammatory interstitial lung disease
 - Active inflammatory bowel disease (IBD)
 - Non-active IBD
 - Active inflammatory joint disease
 - Non-active inflammatory joint disease
 - Active psoriasis
 - Non-active psoriasis
 - Active connective tissue disease
 - Non-active connective tissue disease

- ✓ Current/recent medication
 - Low dose corticosteroids
 - High dose (≥ 10 mg/day Prednisolone or eq) corticosteroids
 - Other immunosuppressants (i.e. Anti-TNF- α , MMF, ...)
 - Antibiotics

- ✓ Prior cancer treatment in earlier stage NSCLC
 - Single Modality treatment
 - Multi-Modality treatment
 - Surgery / radiotherapy
 - Previous IO treatment
 - Year of treatment

For each variable category, the physician has to determine whether it had an impact on his/her treatment decision, yes or no. For all variable categories, for whom the answer was yes, the physician has to select the three most important variable categories that impacted his treatment decision.

5 Study Flow Chart

	V1	V2*
Informed consent	X	
Inclusion	X	
Exclusion	X	
Systemic treatment option		X
Variable categories impacting treatment choice		X
Patient demography characteristics		X
Medical history		X
Co-morbidities		X
Autoimmune disease		X
Baseline medications		X
Prior cancer treatment in earlier stage		X
Site characteristics		X

*time of V2 and V1 can coincide. V2 will only be created if V1 is successfully passed.

It is allowed that information is collected retrospectively.

